2. HYPOTHESIS AND OBJECTIVES

2.1. Hypothesis

The study hypothesizes that patients who get oral methadone to help wean off opioids will have shorter ICU length of stay, shorter duration on the ventilator and potentially improved hospital mortality. The study hypothesizes that, there will be increase in the proportion of patients extubated by day 5.

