2.5 Outcomes

a. Primary

Proportion of patients on methadone that get extubated by day number 5 from the date of intubation

b. Secondary

Proportion of patients that develop prolonged QTC after administration of methadone. Others will be ICU length of stay, ICU mortality, hospital length of stay and hospital mortality.

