4.2 Interventions

Pre-intervention period (1 month)

The objective of this period is to standardize the process to improve familiarity to the investigators. Study procedures will be presented to the nurses by oral presentations, printed material, and by email. The information will include detailed explanation of the process of tapering methadone and weaning patients off opiates as stipulated in the study. It will also elaborate more on the process of managing patients that develop clinical opiate withdrawal symptoms.

Intervention period

Following randomization patients will be assigned to the MG or the NG group. For patients randomized to the MG a "non-formulary medication" order will be placed in the electronic medical record to alert nurses to follow the protocol for patients started on Methadone. For those in the NG group usual hospital protocol of weaning opioids will be followed.

The study is completed for each patient once extubated or discharged from ICU, death, comfort care measures, or after 30 days of participation in the study.

We will collect data regarding participants demographic characteristics, comorbidities, main admission diagnosis, use of mechanical ventilation and vasopressors, ICU and hospital LOS, ICU and hospital mortality. Vital signs, focused general examination, LFTs, with normal ICU standard of care will done. However, EKG will be done at baseline and on day 30 if patient is still on methadone. LFTs are only done at baseline. The duration of use of the medication is not expected to cause an increase in LFTs. The listed labs are the only additional labs other than what is usually ordered for standard care in ICU. The information will be collected by reviewing medical records and will be recorded in electronic form only, using REDCap.

#UTHealth Houston

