6. METHODS AND ASSESSMENTS

Based on the assumptions of successful extubation by day 5 of 50% of patients in the methadone group and 20% of patients in the control group and using a two tailed alpha level of 5%, a power of 80% our sample size calculation comparing proportions of two groups yielded 76. A 5% fallout as correction factor was 4 leaving us with a sample size of 80 patients. Statistical methods will include descriptive statistics and time to event analysis. Baseline characteristics will be reported. Data will be collected on a data collection sheet prior to transfer to REDCAPs database (Appendix 6). We will generate Kaplan-Meier curves and for comparison of hazard between groups we will use Cox regression (Cox proportional hazards model). Patients who die will be censored at time of death. Time of weaning will take into consideration only patients who were permanently disconnected from the ventilator. QTc values will be obtained from patient monitors and documented on data collection tool daily.

Randomization tables will be generated using REDCAPs database by study statistician. At the end of the study recorded information from REDCAPs will be exported to STATA for statistical analysis.

#UTHealth Houston

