10. SAMPLE SIZE AND STATISTICAL METHODS

10.1. Determination of Sample Size

Based on the assumptions of successful extubation by day 5 of 50% of patients in the methadone group and 20% of patients in the Non Methadone group and using a two tailed alpha level of 5%, a power of 80% our sample size calculation comparing proportions of two groups yielded 76. A 5% fall out as correction factor was 4 leaving us with a sample size of 80 patients.

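### The day-5 primary outcome counts any extubation, the sample size assumes successful extubation, and no section says how to score reintubation or extubation for comfort care

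*Combined protocol and SAP*

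**What the plan says.** The event of interest is worded differently in different places.

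- **Primary outcome, section 2.5:** "Proportion of patients on methadone that get extubated by day number 5 from the date of intubation". The hypothesis in section 2.1 is equally unqualified: "there will be increase in the proportion of patients extubated by day 5". Section 1.2 says the same.
- **Sample size, section 10.1 (repeated in section 6):** "successful extubation by day 5 of 50% of patients in the methadone group and 20% of patients in the Non Methadone group". The word *successful* appears here and is not defined.
- **Time-to-event analysis, section 6:** "Time of weaning will take into consideration only patients who were permanently disconnected from the ventilator". Deaths are censored at the time of death.
- **End of participation, section 4.2:** "The study is completed for each patient once extubated or discharged from ICU, death, comfort care measures", or 30 days. Comfort care ends participation, but the section does not say how such a patient is scored.

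No section gives a reintubation window, a requirement to be alive at day 5, or a rule for extubation for comfort care. The data collection tool in Appendix 6, as shown, has no field for reintubation or for the reason for extubation.

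**The concern.** The 50% and 20% rates, and the 80% power built on them, belong to an event that the primary outcome does not define. Under section 2.5 as written, a patient extubated on day 4 and reintubated the next day is a success. A patient extubated for comfort care by day 5 can also be scored as one.

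The comfort-care gap reaches the time analysis too. Such a patient has left the ventilator for good. Because only death is stated as censored, the extubation that precedes it can be read as a weaning event.

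Several features of this trial make the gap more than a drafting matter:

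- Entry requires at least one failed spontaneous breathing trial (section 3.3), so failed extubation is a realistic event.
- Treating physicians and nurses are unblinded (sections 6.1 and 7.5). Blinded outcome assessors cannot correct the timing of an extubation decided by unblinded staff.
- Methadone stops at extubation (section 5.1), but the package insert in Appendix 3 gives a half-life of 8 to 59 hours and a late, long-lasting respiratory depressant effect. Failure rates could therefore differ by arm.

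Counting every extubation could then show a benefit where lasting liberation from the ventilator is unchanged.

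**Working it through.** **1. The plan's own figure.** Inputs from section 10.1: p1 = 0.50, p2 = 0.20, two-sided alpha 0.05, power 0.80. Allocation is 1:1 (section 4.1).

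- Pooled-variance formula: n per arm = [1.96·√(2·0.35·0.65) + 0.842·√(0.50·0.50 + 0.20·0.80)]² / 0.30² = 38.48, so 39 per arm and 78 in total.
- Arcsine formula: h = 2·asin√0.50 − 2·asin√0.20 = 0.6435. Then n = 2·(1.96 + 0.842)² / h² = 37.9, so 38 per arm and 76 in total, as stated.
- Dropout: 76 / 0.95 = 80, as stated.

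The arithmetic is sound. The question is which event the rates describe.

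**2. Method for the scenarios.** Power is exact: binomial probabilities summed over all pairs of counts at 38 per arm for which the uncorrected chi-square test is significant at two-sided 5%. At 50% v 20% this gives 80.0%. Success and raw extubation are linked by raw rate = success / (1 − failure), where failure is the share of extubations that do not last. **All failure rates below are assumed; the documents give none.**

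**3. Lasting success equal, failure differs by arm.** Lasting success is 30% in both arms, and control failure is 10%.

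- Control raw rate: 0.30 / 0.90 = 33.3%.
- Methadone with 20% failure: 0.30 / 0.80 = 37.5%. False difference 4.2 points; rejection rate 6.6%.
- Methadone with 25% failure: 0.30 / 0.75 = 40.0%. False difference 6.7 points; rejection rate 9.1%.
- Significant results favouring methadone rise from about 2.5% to 5.6-8.6%.

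**4. Failure equal in both arms.**

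| Reading of 50% / 20% | Failure in each arm | Rates tested | Power |
|---|---|---|---|
| Raw rates; test lasting success | 10% | 0.50·0.90 = 45% v 0.20·0.90 = 18% | 73.8% |
| Raw rates; test lasting success | 20% | 0.50·0.80 = 40% v 0.20·0.80 = 16% | 66.5% |
| Successful rates; test any extubation | 10% | 0.50/0.90 = 55.6% v 0.20/0.90 = 22.2% | 86% |
| Successful rates; test any extubation | 20% | 0.50/0.80 = 62.5% v 0.20/0.80 = 25% | 92% |

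In the last two rows the observed difference grows from 30 to 33-38 points because failed extubations are counted. The extra power is for the wrong event.

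**5. Comfort-care extubations added equally to both arms.** Adding 5 or 10 points gives 55% v 25% or 60% v 30%. Power is 77.2% or 76.1% at 38 per arm, and 80.2% or 79.6% at the planned 40 per arm.

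**The case against.** The strongest reply is that the intended meaning is plain: the calculation for the primary outcome says *successful*, so a reader would apply that word to section 2.5. This is a fair guess at intent. It does not settle the analysis, because *successful* has no definition to apply.

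Four stronger readings might be inferred, and the documents do not support them.

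- **That sections 6 and 10.1 exclude both reintubated and comfort-care patients, while only 2.5 admits them.** An undefined *successful* excludes nothing for certain, and a comfort-care extubation is a permanent disconnection. The gap runs through all of these sections.
- **That the plan holds three competing definitions of the day-5 outcome.** The sentence on permanent disconnection governs time of weaning. For the day-5 proportion, the direct conflict is between any extubation and successful extubation.
- **That section 2.5 plans a one-arm or as-treated proportion because it names only patients on methadone.** Section 10.1 compares two groups and the trial is randomised. The phrase is loose drafting.
- **That the mismatch must cost power.** With equal failure, power can fall or rise, depending on what 50% and 20% describe. Comfort-care extubations spread equally over the arms cost almost nothing at 40 per arm. Many such events by day 5 also sit awkwardly with entry criteria that require more than 72 hours of ventilation, reversal of the cause and haemodynamic stability.

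The scenario with higher failure on methadone is likewise an assumption. It shows what the wording permits, not what is expected.

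**Conclusion.** The point holds. The primary outcome and hypothesis count any extubation by day 5, the power refers to an undefined successful extubation, and no section covers reintubation or comfort-care extubation. A next-day reintubation is a success under section 2.5 as written. A comfort-care extubation can be one there, and can also be an event in the Cox analysis; that second part is a silence in the plan, not a stated rule.

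Neither the size nor the direction can be fixed from the documents. Under the assumed rates, unequal failure can inflate type I error to 6.6-9.1%. Equal failure leaves power of 74-67% for lasting success if 50% and 20% are raw rates, or raises nominal power to 86-92% if they are successful rates. The case for a change rests on the undefined event in an open-label trial, not on any one of these figures. It should be settled before analysis.

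**What to change.** Use one definition of the day-5 outcome in sections 2.1, 2.5, 6 and 10.1 (and section 1.2, where the hypothesis is repeated), compared by randomised arm in all randomised patients:

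- alive and off invasive ventilation at the day-5 reading;
- no reintubation within a window that the sponsor sets in advance;
- death and extubation for comfort care counted as non-success.

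Apply the same reintubation and comfort-care rules to the weaning event in the Cox analysis. Confirm that 50% and 20% refer to this definition, or restate the power.

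The cost is more than wording. Appendix 6 needs fields for reintubation and reason for extubation. Chart follow-up must run through the reintubation window, although section 4.2 ends participation at extubation. Observed success rates in each arm will be somewhat lower than with all extubations counted.

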2.3. Secondary Objectives

To assess the safety of methadone administration in critically ill patients while in the hospital.

To determine hospital length of stay from the time of enrollment to the time of discharge

2.4. Potential Risks and Benefits:

a. End Points – Efficacy

The study might show the efficacy and potency of methadone in decreasing the length of stay in ICU and duration of mechanically intubation in critically ill patients.

b. End Points - Safety

Adverse events that could be anticipated during the study include signs of opioid withdrawal, elevated liver enzymes, ileus, hypotension and QTC prolongation. Adverse events will be reported in the adverse events registry.

The only two adult studies reported on the use of methadone to wean opioids on mechanical ventilation showed that the much-anticipated risk of QTC prolongation was similar in both patients who received methadone and those that did not receive methadone as shown in the study by Wanzuita et al and Al-Qadheeb et al. [5] Methadone was well tolerated in both studies.

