3.4. Exclusion Criteria

All subjects meeting any of the exclusion criteria at baseline will be excluded from participation.

- 1. Patients with history of opioid drug abuse
- 2. Patients receiving schedule II narcotics on a chronic basis for longer than 6 months prior to ICU admission or on other analgesic infusions other than Fentanyl or Hydromorphone
- 3. Patients with cervical spinal cord injury or neuromuscular disease
- 4. Patients with end stage liver disease at ICU admission (ie, International normalized ratio ≥2and not taking warfarin and/or a total serum bilirubin ≥1.5 times above normal limits
- 5. Patients with prolonged QTc interval ≥500
- 6. Patients with prior history of cardiac conduction defects or suddendeath
- 7. Patients with QTc increase of ≥60 milliseconds above the value of prior EKGs measured during current ICU admission
- 8. Patients with more than 5 days on IV analgesia
- 9. Patients intubated for more than 30 days
- 10. Patients without feeding tubes
- 11. Patients not receiving enteral feeding
- 12. Exclusion of patients in a comatose state
- 13. Exclusion of patients in Status Epilepticus
- 14. Exclusion of post-operative patients

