8. SAFETY MEASUREMENTS

Any adverse events encountered will be documented in the patients' chart once it is noted. These include QTc >500, high grade arrhythmias such as ventricular tachycardia, hypotension and elevated Liver function testing more than 2.5 times the upper limit of normal.

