Bone or Joint aches If patient was having pain previously, only the additional component attributed to opiates withdrawal is scored O not present mild diffuse discomfort patient reports severe diffuse aching of joints/muscles patient is rubbing joints or muscles and is unable to sit still because of discomfort	Gooseflesh skin 0 skin is smooth 3 piloerrection of skin can be felt or hairs standing up on arms 5 prominent piloerrection			
Runny nose or tearing Not accounted for by cold symptoms or allergies 0 not present 1 nasal stuffiness or unusually moist eyes 2 nose running or tearing 4 nose constantly running or tears streaming down cheeks	Total Score The total score is the sum of all 11 items Initials of person completing assessment:			

Score: 5-12 = mild; 13-24 = moderate; 25-36 = moderately severe; more than 36 = severe withdrawal This version may be copied and used clinically.

Journal of Psychoactive Drugs

[figure not shown]
Volume 35 (2), April - June 2003

Source: Wesson, D. R., & Ling, W. (2003). The Clinical Opiate Withdrawal Scale (COWS). J Psychoactive Drugs, 35(2), 253–9.

Appendix 5

Protocol Flow

Appendix 6

#UTHealth Houston

Data Collection Tool

Patient Identification Code (MRN):

Baseline Characteristics Age (years) Sex		
Sex		
Race		
Weight (Kg)		
Duration on ventilator at time of		
randomization (Hours)		
	Pneumonia = 1	
, , ,	Aspiration = 2	
	Non-Pulmonary Sepsis = 3	
	COPD Exacerbation = 4	
	Other Causes = 5	
Assessments and Measurements	Other Causes - 5	
APACHE II Score		
Total SOFA Score		
Tidal Volume ml/kg of predicted		
body weight		
Peep at time of enrollment (cm H2O)		
PaO2: FIO2 ratio (mmHg)		
FiO2 at time of enrollment		
Duration on mechanical ventilation		
before start of weaning(hours)		
Last recorded Ph prior to enrollment		
Duration in ICU stay after enrollment		
(Hours)		
Mean QTc while on Methadone		
Clinical Opiate Withdrawal Scale		
(COWS) after extubation		
Adverse Event		
Medication Parameters		
Fentanyl Initial Dose (mcg/hour)		
Fentanyl accumulated dose(mcg)		
Days on Fentanyl before start of		
weaning		
Hydromorphone initial Dose		
(mg/hour)		
Hydromorphone accumulated		
dose(mg)		
Days on Hydromorphone before		
start of weaning		
Dexmedetomidine accumulated		
dose(mcg)		
Midazolam accumulated dose(mg)		
Propofol accumulated dose (mg)		
Ketamine accumulated dose (mg)

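### The secondary QTc outcome is worded and recorded for methadone patients only and never defines prolongation, so as written it cannot separate a methadone effect from background

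*Combined protocol and SAP*

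**What the plan says.** Section 2.3 gives as a secondary objective "To assess the safety of methadone administration in critically ill patients while in the hospital". The matching outcome in section 2.5b is the "Proportion of patients that develop prolonged QTC after administration of methadone". It has no control-arm counterpart, threshold, baseline rule or time window.

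The other places that bear on QTc are:

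- **Appendix 6 (data collection tool):** the one QTc entry is "Mean QTc while on Methadone".
- **Section 4.2:** "EKG will be done at baseline and on day 30 if patient is still on methadone".
- **Section 6:** "QTc values will be obtained from patient monitors and documented on data collection tool daily". No arm is named.
- **Section 3.4 (exclusions):** a QTc of 500 or more, and separately "Patients with QTc increase of ≥60 milliseconds above the value of prior EKGs measured during current ICU admission".
- **Section 8 (adverse events to be charted):** "These include QTc >500, high grade arrhythmias such as ventricular tachycardia". This list is not linked to the outcome in 2.5.
- **Section 10.2:** states that no safety analysis will be carried out, and names a chi-squared test for categorical variables in general without mentioning QTc.

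**The concern.** Critically ill ventilated patients can develop a long QTc for reasons other than the study drug. The documents show this themselves: Appendix 2 lists haloperidol, quetiapine and olanzapine for refractory agitation or delirium, and the label in Appendix 3 names some neuroleptics among drugs that may prolong the QT interval. A proportion counted only in methadone patients mixes that background with any drug effect and gives up the randomised comparison that could separate them.

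Section 2.4b supports the safety of methadone by citing earlier studies in which the "risk of QTC prolongation was similar in both patients who received methadone and those that did not receive methadone". That is a two-arm statement. The outcome in 2.5, as worded, could neither confirm nor contradict it.

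The consequence is practical. If control QTc values are not asked for during the trial, they may be hard to recover afterwards, and a secondary objective would end with a number that cannot be interpreted.

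**Working it through.** **1. The plan's own figure.** The only sample size is for extubation by day 5 (section 10.1: 50% against 20%, two-sided 5%, power 80%, giving 76, then 80). With the pooled formula, n per arm = [1.96·√(2·0.35·0.65) + 0.8416·√(0.25 + 0.16)]² / 0.30² = 38.5, so 39 per arm or 78 in total. The arcsine version gives exactly 76, and 76/0.95 = 80. The figure reproduces, but no size or rate is stated for QTc. With 1:1 allocation there are 40 patients per arm.

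**2. What the one-arm figure would tell us.** The background rate is an assumption. At 10% to 20%, 0.10 × 40 = 4 to 0.20 × 40 = 8 methadone patients would be counted with no drug effect. Exact (Clopper-Pearson) 95% intervals, with limits Beta(0.025; x, n−x+1) and Beta(0.975; x+1, n−x):

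- 4/40 = 10%: 2.8% to 23.7%
- 8/40 = 20%: 9.1% to 35.6%

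These intervals describe the methadone arm only. An observed 20% means an excess of 15 points if the background is 5%, no excess if it is 20%, and a deficit of 10 points if it is 30%. Nothing in the outcome chooses between these.

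**3. Whether the form can produce the outcome.** The outcome is a proportion, and the form holds one mean per patient. As an illustration, four daily readings of 400 and one of 501 give (4 × 400 + 501)/5 = 420.2. The reading above 500 cannot be seen in the mean. As reproduced, Appendix 6 has no baseline, daily or maximum QTc field, although section 6 says daily values are documented on the tool.

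**4. Why the missing definition matters.** The protocol uses three QTc criteria for other purposes: 500 or more, above 500, and a rise of at least 60 ms. They classify patients differently. A change from 400 to 490 is a rise of 90 ms but is not above 500. A change from 495 to 501 is above 500 but is a rise of only 6 ms.

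**5. What a two-arm version could achieve.** Power = Φ{[d·√n − 1.96·√(2p̄(1−p̄))] / √(p₁(1−p₁) + p₂(1−p₂))}, with n = 40 per arm, d = p₁ − p₂ and p̄ the mean of the two rates. Control rates are assumed. The last column is 1.96·√(2p(1−p)/40), with both arms at the control rate.

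| Control rate | Smallest increase with 80% power | 95% CI half-width if no difference |
|---|---|---|
| 5% | 22.9 points | 9.6 points |
| 10% | 26.0 points | 13.1 points |
| 15% | 28.1 points | 15.6 points |
| 20% | 29.4 points | 17.5 points |
| 30% | 30.8 points | 20.1 points |

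At 38 per arm the detectable increase is 23.7 to 31.6 points. At 40 per arm, power is 24% for 10% against 20%, and 61% for 10% against 30%.

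**The case against.** The best defence is that the wording is loose and a two-arm comparison is meant. The primary outcome in 2.5 is also phrased for patients on methadone, yet sections 6 and 10.1 size it as a two-group comparison. Sections 6.1 and 7.5 blind the assessors of primary and secondary outcomes to group, which makes sense only if both groups are assessed. Section 1.2a plans to compare ICU outcomes, section 6 does not restrict daily monitor QTc to one arm, and section 10.2 has a general test for categorical data. Appendix 6 is also incomplete for other outcomes, so it is weak evidence of intent.

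Much of this stands as evidence of intent. It does not repair the outcome. The primary has an explicit two-group calculation behind it, whereas QTc has none. The form asks for no control values, and section 10.2 disclaims a safety analysis.

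Three stronger readings are tempting, and the documents do not support them:

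- A reader might infer that the outcome compares a baseline ECG with later monitor readings, so that a device difference would pass for a drug effect. No section defines such a comparison or any change from baseline. What can be said is that the source is mixed and unspecified.
- A reader might take above 500 as the definition of an event. That figure sits in the adverse-event list only.
- A reader might think QTc is not followed until day 30. Section 6 has it recorded daily, which largely answers the point.

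**Conclusion.** The concern holds for the outcome as worded. It gives a one-arm proportion, with prolongation undefined, the QTc source inconsistent, and a form field that cannot produce the statistic. Beside it stands a statement that safety will not be analysed, although safety is a secondary objective.

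A reader might go further and conclude that the trial cannot show whether methadone prolongs QTc. That is too strong. Daily monitor values are not confined to one arm, so a same-source comparison is possible if control values are recorded.

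The 4 to 8 patients counted with no drug effect rest on an assumed 10% to 20% background rate, and the detectable increases of about 23 to 31 points on assumed control rates of 5% to 30%. Even a repaired outcome will therefore only estimate the difference, and a null result should not be read as evidence of safety.

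**What to change.** 1. **Outcome (2.5b).** Define it in each randomised arm as the proportion with any QTc above 500 ms or a rise of at least 60 ms over baseline, both being thresholds the protocol already uses.
2. **Source.** Take baseline and follow-up from the same source: the daily monitor values of section 6, with a monitor reading on the day of randomisation as baseline. Keep the conditional day-30 ECG out of this outcome.
3. **Form (Appendix 6).** Replace the mean with baseline and daily (or maximum) QTc fields completed for every patient. Renaming the mean field would not be enough.
4. **Window.** Use the same window after randomisation in both arms, up to the end of participation, and report days observed per arm. Section 4.2 ends participation at extubation, and the plan assumes 50% against 20% extubated by day 5. If that assumption is right, methadone patients would tend to be observed for fewer days, and their proportion would be low for that reason alone.
5. **Analysis (10.2).** Report the between-arm difference with a 95% confidence interval as an estimate, and reconcile the statement on safety analysis with sections 2.3 and 2.5.

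The cost is outcome wording, form fields and daily transcription for control patients. It assumes monitor QTc is available for them, which section 6 implies but does not state.
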